## **6 Treatment**

### **6.1 Study treatment**

#### **6.1.1 Investigational and control drugs**

The following investigational treatment will be supplied by Novartis to the study sites:

- Name: fevipiprant (labeled as QAW039)
- Formulation: tablet
- Unit dose: 2 strengths: 150 mg and 450 mg

Please refer to the Investigator's Brochure for composition of the fevipiprant tablets.

- Name: fevipiprant placebo
- Formulation: tablet
- Unit dose: matching placebo to fevipiprant 150 mg, matching placebo to fevipiprant 450 mg

Please refer to the Investigator's Brochure for composition of the placebo tablets.

The investigational treatment (tablets) will be supplied in bottles. The matching placebos for fevipiprant will be identical in appearance to their active counterparts and will be identically packaged.

#### **6.1.2 Additional study treatments**

At the start of the Run-in period, all patients will be provided with mometasone furoate nasal spray (no specific brand required) as the SoC for use during the study. This will either be supplied to the Investigator sites by Novartis or sourced locally and reimbursed by Novartis. All patients will remain on their current asthma treatment for the duration of the study (with the exception of LTRAs, which should be discontinued prior to patients entering the Run-in period). Patients will also be provided with short-acting  $\beta_2$ -agonists (SABAs), (salbutamol/albuterol/other SABA) which they will be instructed to use throughout the study as rescue medication to treat asthma symptoms on an 'as needed basis'. SABAs will either be supplied to the Investigator sites by Novartis or sourced locally and reimbursed by Novartis.

Should patients develop any sino-nasal exacerbations during the course of the study, the treating physician should follow their normal treatment regimen with systemic corticosteroids and/or antibiotics.

#### **6.1.3 Treatment arms/group**

Subjects will be assigned at the randomization visit to one of the following 3 treatment arms in a ratio of 1:1:1.

During the Run-in period, all patients will receive the NP SoC treatment only - Mometasone Furoate 200  $\mu\text{g}$  once daily, administered as two 50  $\mu\text{g}$  actuations into each nostril.

For the treatment period, patients will be assigned to one of three treatment arms as follows in a 1:1:1 ratio:

- QAW039 150 mg once daily (one tablet of blinded QAW039 at 150 mg dosage strength to be given together with one tablet blinded placebo to QAW039 450 mg).
- QAW039 450 mg once daily (one tablet of blinded QAW039 at 450 mg dosage strength to be given together with one tablet blinded placebo to QAW039 150 mg).
- Placebo to QAW039 once daily (one tablet blinded placebo to QAW039 150 mg and one tablet blinded placebo to QAW039 450 mg).

Patients will be instructed to take their investigational treatment (QAW039 or placebo) once daily in the morning without regard to time of food intake.

#### 6.1.4 Treatment duration

The planned duration of the study treatment period is 16 weeks from the point of randomization. Subjects will take their assigned study treatments along with the NP SoC which will be supplied to patients at the start of the Run-in period. The patients will administer the SoC only, during the Run-in period and then administer both the SoC and the study treatment, during the 16-week Treatment period.

### 6.2 Other treatment(s)

All patients will be provided with short-acting  $\beta$ 2-agonists (SABAs) (salbutamol/albuterol/other SABA) which they will be instructed to use throughout the study as rescue medication on an ‘as needed basis.’

#### 6.2.1 Concomitant therapy

All medications, procedures and significant non-drug therapies (including physical therapy and blood transfusions) administered after the subject was enrolled into the study must be recorded on the appropriate Case Report Forms (CRFs). The medications in [Table 6-1](#) are only permitted under the circumstances given and this table is not considered all-inclusive.

Each concomitant drug must be individually assessed for adherence to the indication and against all exclusion criteria/prohibited medication. If in doubt the Investigator should contact the Novartis/sponsor medical monitor before randomizing a subject or allowing a new medication to be started. If the subject is already enrolled, contact Novartis/sponsor to determine if the subject should continue participation in the study.

**Table 6-1 Medications allowed under certain conditions**

Class of medication	Conditions
Short-acting $\beta$ 2-agonist (SABA)	Rescue medication to be taken as needed
SCS for treatment of symptoms of asthma or NP	One treatment of up to 5 consecutive days allowed during the study. SCS should not be administered within the 2 weeks prior to nasal endoscopy
Maintenance Immunotherapy for allergies	Stable dose for at least 3 months prior to Screening and the dose remains stable throughout the study
Inactivated influenza vaccine, pneumococcal vaccine or any other inactivated vaccine	Not administered with 48 hour prior to a study visit
Topical corticosteroids for treatment of eczema	Recommended doses and dosage regimens

Class of medication	Conditions
Antihistamines (e.g. loratadine, cetirizine)	Stable for at least 1 month prior to Screening visit and dose remains stable throughout the study
Nasal anticholinergic	Treatment regimen has been stable for at least 1 month prior to Screening visit. In the case of as needed use, providing an established pattern of use, has been documented
Nasal or ophthalmological preparations of nedocromil	
Nasal or ophthalmological preparations of antihistamines	

### 6.2.2 Prohibited medication

Use of the treatments displayed in the below table is NOT allowed after screening. Each concomitant drug must be individually assessed against all exclusion criteria and the tables below to see if it is allowed. If in doubt, the Investigator should contact the Novartis medical monitor or designee before randomizing a patient or allowing a new medication to be started. This table is not considered all-inclusive. Medications should be assessed for adherence to the indication and other inclusion/exclusion criteria. These medications are also prohibited if administered for other indications.

**Table 6-2 Prohibited Medication**

Medication	Prohibition period (Minimum cessation prior to Run-in)
Other investigational drugs	30 days or 5 half-lives, whichever is longer
Oral and Nasal Decongestants (more than 3 weeks total use)	30 days
Live attenuated vaccine	30 days
Simvastatin > 20 mg, atorvastatin > 40 mg, pravastatin > 40 mg, or pitavastatin > 2 mg total daily dose	7 days
Other DP2 antagonists (e.g., ramatroban)	7 days or 5 half-lives whichever is longer
Short-acting anticholinergics	8 hours
Fixed combinations of short-acting $\beta_2$ agonists and short-acting anticholinergics	8 hours
Systemic mast cell stabilizers (e.g., cromoglycate, nedocromil, ketotifen)	7 days
Monoclonal antibodies, investigational or approved, for the treatment of asthma (e.g., omalizumab)	6 months
Nasal corticosteroids in the form of drops, sprays that are administered via devices (e.g. OptiNose device or stents) or lavage	8 weeks
Tetracyclic or macrolide antibiotics	8 weeks
Rifampin, probenecid, ritonavir and valproic acid (i.e. medications blocking several pathways important for the elimination of QAW039 (broad range UGT inhibition and/or inhibition of OAT3, OATP1B3, MXR and P-gp)).	7 days
Methotrexate, gold salts, cyclosporine, troleandomycin, azathioprine, other immunomodulator drugs or immuno-modulatory monoclonal antibodies	6 months
Systemic (oral, intravenous, intramuscular) corticosteroids for non-asthma conditions	3 months

Medication	Prohibition period (Minimum cessation prior to Run-in)
Leukotriene receptor antagonists (LTRA)	Stopped at beginning of Run-in period

### 6.2.3 Rescue medication

At the start of the Run-in period, all patients will be provided with a SABA (such as salbutamol 100 mcg or albuterol 90 mcg) which they will be instructed to use throughout the study as rescue medication on an ‘as needed basis’. Patients will be advised that between visits they could take their rescue medication for symptoms of asthma. Rescue medication (i.e., SABAs) will either be supplied to the Investigator sites locally by the Novartis country pharma organization (CPO) or sourced locally and reimbursed by Novartis. Nebulized salbutamol/albuterol is not allowed as rescue medication and will not be supplied.

Should patients develop any sino-nasal exacerbations during the course of the study, the treating physician should follow their normal treatment regimen with systemic corticosteroids and/or antibiotics. Short term oral or nasal decongestants may also be utilised as a rescue therapy however the assessment of NPS must not be performed within 3 days of their use.

Use of rescue medication must be recorded on the concomitant medications in the CRF.

## 6.3 Subject numbering, treatment assignment, randomization

[figure not shown]
### 6.3.1 Subject numbering

Each subject is identified in the study by a Subject Number (Subject No.), that is assigned when the patient is first enrolled for screening and is retained as the primary identifier for the subject throughout his/her entire participation in the trial. The Subject No. consists of the Center Number (Center No.) (as assigned by Novartis to the investigative site) with a sequential subject number suffixed to it, so that each subject is numbered uniquely across the entire database. Upon signing the informed consent form, the patient is assigned to the next sequential Subject No. available.

### 6.3.2 Treatment assignment, randomization

At randomization visit, all eligible subjects will be randomized via Interactive Response Technology (IRT) to one of the treatment arms. The Investigator or his/her delegate will contact the IRT after confirming that the patient fulfills all the inclusion/exclusion criteria. The IRT will assign a randomization number to the patient, which will be used to link the patient to a treatment arm and will specify unique medication numbers for the first packages of study drug to be dispensed to the patient. The randomization number will not be communicated to the caller.

The randomization numbers will be generated using the following procedure to ensure that treatment assignment is unbiased and concealed from subjects and Investigator staff. A patient randomization list will be produced by the IRT provider using a validated system that automates the random assignment of patient numbers to randomization numbers. These randomization numbers are linked to the different treatment arms, which in turn are linked to medication numbers. A separate medication list will be produced by or under the responsibility of Novartis Global Clinical Supplies using a validated system that automates the random assignment of medication numbers to packs containing the investigational drug(s).

The randomization scheme for subjects will be reviewed and approved by a member of the Randomization Group.

## 6.4 Treatment blinding

Subjects, Investigator staff, persons performing the assessments, and clinical trial team (CTT) will remain blind to the identity of the treatment from the time of randomization until database lock, using the following methods: (1) Randomization data are kept strictly confidential until the time of unblinding, and will not be accessible by anyone else involved in the study, (2) the identity of the treatments will be concealed by the use of study treatment that are all identical in packaging, labeling, schedule of administration, appearance, taste and odor.

A double-dummy design is used because the identity of the study treatment cannot be disguised, as the drug products are visibly different.

Unblinding will occur in the case of subject emergencies and at the conclusion of the study.

**Table 6-3 Blinding and unblinding plan**

Role	Time or Event		
	Randomization list generated	Treatment allocation & dosing	Safety event (single subject unblinded)
Subjects	B	B	B
Site staff	B	B	B
Unblinded site staff e.g. pharmacy staff ( specify )	B	B	B
Drug Supply and Randomization Office	UI	UI	UI
Unblinded Pharmacovigilance sponsor staff	UI	UI	UI
Statistician/statistical programmer/data analysts (e.g. biomarker, PK)	B	B	B
Independent committees used for assessing interim results, if required (e.g. DMC)	NA	NA	NA
All other sponsor staff not identified above (trial team, project team, management & decision boards, support functions)	B	B	B

Key:

[figure not shown]
UI: Allowed to be unblinded on individual subject level

B: Remains blinded

NA: Not applicable to this study

## 6.5 Dose escalation and dose modification

Investigational or other study treatment dose adjustments and/or interruptions are not permitted and should any such changes in dosing regimen occur during the study then the patients will be excluded unless highlighted as a rescue therapy within other sections of the protocol.

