### **6.5.1 Dose modifications**

For subjects who do not tolerate the protocol-specified dosing schedule, dose interruptions and/or reductions are not permitted and the patients will be withdrawn from the study.

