- If a patient undergoes nasal surgery, including but not limited to the following: treatment of nasal polyposis, septal deviation correction, turbinectomy, para-nasal sinus drainage, nasal plastic surgery, hypophysis tumor nasal approach.
- If a patient develops a medical condition, that requires consistent use of prohibited treatment as per [Section 6.2.2](#) or if patient exhibits a behavior of non-compliance regarding prohibited medication.

If discontinuation of study treatment occurs, the Investigator should make a reasonable effort to understand the primary reason for the subject's premature discontinuation of study treatment and record this information.

[figure not shown]
Subjects who discontinue study treatment or who decide they do not wish to participate in the study further should NOT be considered withdrawn from the study UNLESS they withdraw their consent (see withdraw of informed consent section.). **Where possible, they should return for the assessments indicated** in the Assessment schedule ( [Table 8-1](#) ).

After study treatment discontinuation, at a minimum, in abbreviated visits, the following data should to be collected at clinic visits or via telephone visits:

- new/concomitant treatments including OCS use
- adverse events/Serious Adverse Events

If they fail to return for these assessments for unknown reasons, every effort (e.g. telephone, e-mail or letter) should be made to contact the subject/pre-designated contact as specified in the lost to follow-up section. This contact should preferably be done according to the study visit schedule.

If the patient cannot or is unwilling to attend any visit(s), the site staff should maintain regular telephone contact with the patient, or with a person pre-designated by the patient. This telephone contact should preferably be done according to the study visit schedule. The information already collected during the study including your samples will still be used according to applicable laws

The Investigator must also contact the IRT to register the patient's discontinuation from study treatment.

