## 10.2 Additional Safety Monitoring

### 10.2.1 Liver safety monitoring

To ensure subject safety and enhance reliability in determining the hepatotoxic potential of an investigational drug, a standardized process for identification, monitoring and evaluation of liver events has to be followed.

The following two categories of abnormalities / adverse events have to be considered during the course of the study (irrespective of whether classified/reported as AE/SAE):

- Liver laboratory triggers, which will require repeated assessments of the abnormal laboratory parameter
- Liver events, which will require close observation, follow-up monitoring and contributing factors are recorded on the appropriate CRFs

Please refer to [Table 16-1](#) - Appendix 2 in [Section 16](#) for complete definitions of liver laboratory triggers and liver events.

Every liver event defined in [Section 16.1](#)- Appendix 2 should be followed up by the Investigator or designated personnel at the trial site, as summarized below. Additional details on actions required in case of liver events are outlined in [Table 16-2](#) - Appendix 2. Repeat liver function test (LFT) to confirm elevation.

- These liver chemistry repeats will be performed using the central laboratory. If results will not be available from the central laboratory, then the repeats can also be performed at a local laboratory to monitor the safety of the subject. If a liver event is subsequently reported, any local liver chemistry tests previously conducted that are associated with this event should have results recorded on the appropriate CRF.
- If the initial elevation is confirmed, close observation of the subject will be initiated, including consideration of treatment interruption if deemed appropriate.

- Discontinuation of the investigational drug (refer to the Discontinuation of study treatment section), if appropriate
- Hospitalization of the subject if appropriate
- Causality assessment of the liver event
- Thorough follow-up of the liver event should include
- These investigations can include based on Investigator's discretion: serology tests, imaging and pathology assessments, hepatologist's consultancy; obtaining more detailed history of symptoms and prior or concurrent diseases, history of concomitant drug use, exclusion of underlying liver disease

All follow-up information, and the procedures performed must be recorded as appropriate in the CRF

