> 3 to ≤ 5 × ULN (patient is asymptomatic)	
 
Repeat LFT within the next week
 
If elevation is confirmed, initiate close observation of the patient
 
	Investigator discretion Monitor LFT within 1 to 4 weeks
ALP (isolated)		
> 2 × ULN (in the absence of known bone pathology)	
 
Repeat LFT within 48 hours
 
If elevation persists, establish causality
 
Record the AE and contributing factors (e.g., conmeds, med hx, lab) in the appropriate CRF
 
	Investigator discretion Monitor LFT within 1 to 4 weeks or at next visit
TBL (isolated)		
> 2 × ULN (in the absence of known Gilbert syndrome)	
 
Repeat LFT within 48 hours
 
If elevation persists, discontinue the study drug immediately
 
Hospitalize if clinically appropriate
 
Establish causality
 
Record the AE and contributing factors (e.g., conmeds, med hx, lab) in the appropriate CRF
 
	ALT, AST, TBL, Alb, PT/INR, ALP and γGT until resolution c (frequency at Investigator discretion) Test for hemolysis (e.g., reticulocytes, haptoglobin, unconjugated [indirect] bilirubin)
> 1.5 to ≤ 2 × ULN (patient is asymptomatic)	
 
Repeat LFT within the next week
 
If elevation is confirmed, initiate close observation of the patient
 
	Investigator discretion Monitor LFT within 1 to 4 weeks or at next visit
Jaundice	
 
Discontinue the study treatment immediately
 
Hospitalize the patient
 
Establish causality
 
Record the AE and contributing factors (e.g., conmeds, med hx, lab) in the appropriate CRF
 
	ALT, AST, TBL, Alb, PT/INR, ALP and γGT until resolution c (frequency at Investigator discretion)
Any AE potentially indicative of a liver toxicity	
 
Consider study treatment interruption or discontinuation
 
Hospitalization if clinically appropriate
 
Establish causality
 
Record the AE and contributing factors (e.g., conmeds, med hx, lab) in the appropriate CRF
 
	Investigator discretion

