### 16.3 Appendix 3: Specific Renal Alert Criteria and Actions and Event Follow-up

**Table 16-3 Specific Renal Alert Criteria and Actions**

Serum Event	
Serum creatinine increase 25 – 49% compared to baseline	Confirm 25% increase after 24-48h Follow up within 2-5 days
Acute Kidney Injury: Serum creatinine increase ≥50% compared to baseline	Follow up within 24-48h if possible Consider study treatment interruption Consider patient hospitalization /specialized treatment
Urine Event	
Albumin-creatinine ratio (ACR) ≥1g/g or ≥100 mg/mmol; Protein-creatinine ratio (PCR ) ≥1g/g or ≥100 mg/mmol	Confirm value after 24-48h Perform urine microscopy Consider study treatment interruption / or discontinuation
For all renal events:	

Document contributing factors in the CRE: co-medication, other co-morbid conditions, and additional diagnostic procedures performed
 
Monitor patient regularly (frequency at investigator's discretion) until either:
 
Event resolution: sCr within 10% of baseline or protein-creatinine ratio within 50% of baseline, or
 
Event stabilization: sCr level with ±10% variability over last 6 months or protein-creatinine ratio stabilization at a new level with ±50% variability over last 6 months.
	

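### Protocol 6.5 and 6.5.1 forbid study-drug interruption and remove the patient, while the safety sections offer interruption and 9.1.1 keeps patients who stop drug in follow-up (minor inconsistency)

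*Protocol*

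**What the plan says.** **The prohibition.** Protocol 6.5 states that "interruptions are not permitted and should any such changes in dosing regimen occur during the study then the patients will be excluded". Its only exception is for rescue therapy. Section 6.5.1 adds, of any patients that "do not tolerate the protocol-specified dosing schedule, dose interruptions and/or reductions are not permitted and the patients will be withdrawn from the study".

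**The safety sections.** Section 10.2.1 provides, for a confirmed liver test elevation, for close observation "including consideration of treatment interruption if deemed appropriate", and separately lists "Discontinuation of the investigational drug (refer to the Discontinuation of study treatment section), if appropriate". Table 16-2, for an adverse event suggesting liver toxicity, says "Consider study treatment interruption or discontinuation". Table 16-3, for a urine albumin or protein event, says "Consider study treatment interruption / or discontinuation". Its row for a creatinine rise of at least 50% reads "Follow up within 24-48h if possible Consider study treatment interruption Consider patient hospitalization /specialized treatment".

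**Status after stopping drug.** Section 9.1.1 says that patients who discontinue study treatment "should NOT be considered withdrawn from the study UNLESS they withdraw their consent", and asks them to return for scheduled assessments where possible. The glossary defines premature subject withdrawal as the point after which drug is stopped and no assessments are planned.

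**The analysis sections.** Protocol 12.3 and SAP 2.4.1.1 summarise interruptions, and SAP 2.4.1.2 allows for their length when calculating compliance. Neither the full analysis set (FAS) definition (Protocol 12.1, SAP 2.2) nor the exclusion list in SAP 5.5 mentions interruption.

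**The concern.** A site that pauses study drug for a renal or liver signal takes an action that one part of the protocol offers and another forbids. A site that stops drug for intolerance finds one section telling it to withdraw the patient from the study and another telling it not to.

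At stake is the Week 16 NPS. Endoscopy is scheduled only twice after baseline, at Weeks 8 and 16. If a site ends follow-up under 6.5.1 where another would continue it under 9.1.1, whether the primary endpoint is observed depends on which section the site read. Such a loss would be avoidable, because the protocol already describes how to keep these patients in follow-up.

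**Working it through.** **1. Interruption.**

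| Situation | Dosing options in the safety text | Can a site also comply with 6.5? |
|---|---|---|
| Confirmed liver test elevation (10.2.1) | Interrupt or discontinue | Yes, by stopping drug permanently |
| AE suggesting liver toxicity (Table 16-2) | Interrupt or discontinue | Yes, by stopping drug permanently |
| Urine albumin or protein event (Table 16-3) | Interrupt or discontinue | Yes, by stopping drug permanently |
| Creatinine rise of at least 50% (Table 16-3) | Interrupt only | Not by taking the listed action |

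Every row says to consider the action, and none requires it. The rescue-therapy exception in 6.5 does not cover pausing study drug for a safety signal.

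**2. Follow-up.** Section 6.5.1 applies to patients who do not tolerate dosing. Its withdrawal wording, read with the glossary, ends assessments. Section 9.1.1 continues them unless consent is withdrawn. For a patient who stops drug because of intolerance, these are opposite instructions. Section 6.5 is only ambiguous: it gives no object for the exclusion.

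**3. Which endpoint values could be lost.** Table 8-1 gives:
- on-treatment chemistry at Days 56 and 112;
- post-baseline endoscopy at Days 56 and 112;
- no on-treatment urinalysis;
- liver and renal event monitoring at every visit.

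A patient who leaves early has a final visit as soon as possible (Protocol 8), and the end-of-treatment/discontinuation column of Table 8-1 includes endoscopy. SAP 2.1.3.10 lets that visit replace a missed scheduled visit if it lies closer to that visit's planned day than to any other.

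- Event found on Week 16 chemistry: the Week 16 NPS is due at the same visit, so nothing is lost.
- Event found on Week 8 chemistry: the Week 8 NPS is normally in hand. To count as Week 16, the discontinuation visit must fall after Day (84 + 112)/2 = 98, which is 98 − 56 = 42 days after Week 8. If only endoscopy visits count for remapping, the cut-off is Day (56 + 112)/2 = 84, or 28 days after Week 8. A prompt final visit would miss either cut-off, so the Week 16 NPS, one of the two post-baseline values, is lost.
- Stop before Week 8: a discontinuation visit after Day (28 + 56)/2 = 42 can be remapped to Week 8, so an early stop need not lose both values.

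**4. Effect on power.** Inputs from Protocol 12.8.1: difference 1.5, SD 1.8, one-sided alpha 0.0125, 31 per arm, 10% dropout. Completers per arm: 31 × 0.9 = 27.9, about 28. One lost value is 1/28 = 3.6% of an arm.

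Two-sample t-test on completers, with noncentrality 1.5 / (1.8 × √(1/n₁ + 1/n₂)):

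| Active vs placebo completers | Noncentrality | Power |
|---|---|---|
| 28 vs 28 | 3.118 | 78.9% |
| 27 vs 28 | 3.090 | 78.1% |
| 26 vs 28 | 3.060 | 77.2% |

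Each lost value costs a little under one percentage point. The repeated-measures model recovers part of that from Week 8.

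**The case against.** The best defence is that the protocol uses its withdrawal wording loosely and already shows how to read it. Section 6.6.2 says a patient whose code is broken in an emergency is withdrawn from the study, yet 9.1.1 lists the same event, with a cross-reference to 6.6.2, among reasons to discontinue study treatment. The corticosteroid bullet in 9.1.1 also speaks of withdrawal under that heading. On this view 6.5.1 only means stopping drug, and 9.1.1 governs the rest. This carries weight: sites may well follow 9.1.1 already. It remains an inference, because no text says so for 6.5.1 and the glossary points the other way.

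It is also fair that a compliant route exists even for the creatinine row. Section 9.1.1 requires discontinuation when continuing would harm the patient's risk/benefit balance.

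A reader might infer four stronger points, none of which the documents support:

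- **Every laboratory-triggered interruption ends follow-up.** The withdrawal wording of 6.5.1 covers only intolerance of dosing. Section 6.5 does not say what the patient is excluded from.
- **These patients leave the primary analysis.** Neither the FAS definition nor SAP 5.5 removes a patient for an interruption.
- **The missing-at-random assumption fails.** Missingness linked to a safety event breaks it only if, given the observed data, it also depends on the unobserved NPS. Nothing in the documents links creatinine or liver tests to polyp size.
- **Patients are put at risk.** Section 14.1 lets the investigator act at once for safety even where that deviates from the protocol.

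**Conclusion.** The inconsistency is real and nothing in the current text resolves it, but it is minor. It is a fault of wording with a possible cost in endpoint data; the primary analysis itself is not defective. Taken literally, 6.5.1 would forgo an obtainable Week 16 NPS for some patients who stop drug.

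The documents do not give the number of such patients; I assume it is low. The power figures rest on the plan's own design assumptions and a completers t-test, and the change is negligible. Because return under 9.1.1 is only where possible, rewording would recover some of the lost values, not all of them.

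**What to change.** Amend Protocol 6.5 and 6.5.1 to say that:

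- dose reductions are not permitted;
- study-drug interruption is permitted only where Section 10.2.1 or Appendices 2 and 3 provide for it;
- patients who cannot continue dosing are discontinued from study treatment (replacing the exclusion and study-withdrawal wording) and stay in scheduled follow-up under 9.1.1, including Week 8 and Week 16 endoscopy where possible.

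Make the same change of term in 6.6.2 and in the corticosteroid bullet of 9.1.1, so that the loose usage does not survive elsewhere. Whether and when dosing restarts after an interruption is a clinical decision for the sponsor, and the amendment should say who makes it.

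The cost is a protocol amendment with IRB/IEC approval, and health authority approval where required (14.1). The analysis sets and the SAP need no change, since interruptions are already summarised and counted in compliance. The downside is slightly more off-drug time among analysed patients.
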